### **6.3. Assignment to Study Intervention**

Allocation of participants to treatment groups will proceed through the use of an IRT system. The site personnel (study coordinator or specified designee) will be required to enter or select information including but not limited to the user's ID and password, the protocol number, and the participant number. The site personnel will then be provided with a randomization number corresponding to the assigned treatment group, and DU or container number(s) when study intervention is being supplied via the IRT system. The IRT system will provide a confirmation report containing the participant number, randomization number, and DU or container number assigned. The confirmation report must be stored in the site's files.

Randomization will occur in the IRT. Randomization will be stratified by the use of stable prophylactic migraine medications through randomization (yes or no) and country/region.

Study intervention will be dispensed at the Baseline Visit as indicated in the [SoA](#).

The study-specific IRT reference manual and IPM will provide the contact information and further details on the use of the IRT system.

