### 5.2.2. Analyses for Categorical Endpoints

Categorical variables will be summarized as the number and percentage of participants within each category. Percentages in frequency tables are calculated against the number of participants in each treatment group in the specified analysis set. For each endpoint, Mantel-Haenszel risk estimation will be used for the difference in percentages of participants achieving the endpoint response criteria (zavegepant-placebo) stratified by country/region. The difference in percentages between treatment groups will be presented with p-value and asymptotic standard error (ASE) together with a 95% CI based on normal approximation. For individual treatment group, the percentage of participants achieving the endpoint response criteria will be presented with ASE and a 95% CI based on normal approximation.

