### 5.2.3. Time-to-Event Analysis

Time-to-event distribution of endpoints (rescue medication use, pain freedom, MBS freedom, pain relief, normal function, phonophobia absence, photophobia absence, nausea absence) will be tabulated and plotted. Participants are considered to have an event through X hours ( $X=24$  hours or 8 hours) if the first post dose eDiary date/time defining a response is (1) at or before the upper bound of the X-hour analysis window in minutes (see Section 5.2.5), and (2) is before the imputed rescue medication start date/time, if not missing. Otherwise, participants who do not have an event through X hours are censored at the earliest of the following: (1) upper bound of the X-hour analysis window + 1 minute; (2) the imputed first rescue medication start date/time; (3) the last non-missing contact date/time.

For time to rescue medication use through 24 hours, participants are considered to have an event if the date/time of taking the rescue medication is prior to or at 24 hours post dose; otherwise, the time to rescue medication will be considered as censored at the earliest of the following: (1) 24 hours post dose + 1 minute, (2) the last non-missing contact date/time. For time to rescue medication use through 24 hours, the summary table and Kaplan-Meier plot will be using 2-hour time intervals: 0 to <2,  $\geq 2$  to <4,  $\geq 4$  to <6, ...,  $\geq 24$ . For exploratory endpoints through 8 hours, the summary table and Kaplan-Meier plot will be using the following time intervals: 0 to <15,  $\geq 15$  to <30,  $\geq 30$  to <45,  $\geq 45$  to <60,  $\geq 60$  to <90,  $\geq 90$  to <120,  $\geq 120$  to <180,  $\geq 180$  to <240,  $\geq 240$  to <360,  $\geq 360$  to <495, and  $\geq 495$  minutes.

The summary table will include the following statistics: number of participants at risk, number of participants with events, number of participants censored for each time interval; overall number and percentage of participants with events and censored; time-to-event estimate for median, first quartile, and third quartile with corresponding 95% CIs. The 95% CI will be estimated using the method of Brookmeyer and Crowley. The log-rank p-value will also be presented for comparison of zavegepant versus placebo. In the Kaplan-Meier plot, the percentage of participants for the endpoints within the time period postdose on the y-axis versus time in minutes on the x-axis will be displayed.

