#### 6.2.15.2. Supportive Analysis

Time to rescue medication use through 24 hours postdose is assessed by treatment group using the approach as described in Section 5.2.3. Rescue medication use through 24-hours postdose is considered as an event.

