#### 6.4. Subset Analyses

For the co-primary and key secondary endpoints, subgroup analyses will be conducted for the following baseline demographic and characteristic variables:

- Country/region at randomization: China, Korea, Taiwan
- Age at informed consent category 1: <40, ≥ 40

- Sex: male, female
- BMI category:  $<25 \text{ kg/m}^2$ ,  $\geq 25$  to  $<30 \text{ kg/m}^2$ ,  $\geq 30 \text{ kg/m}^2$
- Aura on study before dosing: yes, no
- History of migraine with aura: yes, no (see Section 6.5.1.2)
- Historical number of moderate to severe migraine attacks per month:  $<4$ ,  $\geq 4$  (overall median)
- Stable prophylactic migraine medication use through randomization: yes, no.

For the primary endpoint of “percentage of participants with an MBS reported before dosing that is absent at 2 hours postdose”, the following characteristic variables will additionally be used for subgroup analysis:

- MBS on study before dosing: Nausea
- MBS on study before dosing: Phonophobia
- MBS on study before dosing: Photophobia

Main analysis method described in Section 5.2.2 will be used, except for the subgroup analysis by country/region at randomization, in which Mantel-Haenszel risk estimation without stratification will be conducted.

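### SAP 5.2.3 names no strata for its eight log-rank comparisons, while the main percentage analyses of the same endpoints are stratified by country/region; stratifying the log-rank test too is a free improvement

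*SAP*

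**What the plan says.** SAP 5.2.3 lists the time-to-event endpoints as "rescue medication use, pain freedom, MBS freedom, pain relief, normal function, phonophobia absence, photophobia absence, nausea absence", eight in all, and adds: "The log-rank p-value will also be presented for comparison of zavegepant versus placebo". It mentions no strata. The Appendix 1 time-to-event rows name only the type of analysis, again without strata. SAP 6.2.15.2 sends the rescue-medication analysis back to the same text: "Time to rescue medication use through 24 hours postdose is assessed by treatment group using the approach as described in Section 5.2.3".

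For percentages, SAP 5.2.2 reads: "Mantel-Haenszel risk estimation will be used for the difference in percentages of participants achieving the endpoint response criteria (zavegepant-placebo) stratified by country/region". The matching Appendix 1 rows repeat country/region at randomization as the stratum, and SAP 6.3 applies it to the exploratory percentages as well.

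Protocol 6.3 gives two randomization factors: "Randomization will be stratified by the use of stable prophylactic migraine medications through randomization (yes or no) and country/region". SAP 6.4 lists the levels as "Country/region at randomization: China, Korea, Taiwan". Neither document states enrolment shares, country-specific rates, or power for any log-rank test.

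**The concern.** A log-rank test with no strata named will normally be programmed as unstratified. Where the SAP means a percentage comparison to be unstratified, it says so: for the subgroup analysis by country/region, SAP 6.4 specifies "Mantel-Haenszel risk estimation without stratification will be conducted". Section 5.2.3 has no such statement, so the choice is left open. Low analytic status does not explain the gap, because the exploratory percentages are stratified.

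Randomization within country/region balances the arms on that factor. If the factor also predicts response or rescue, the unstratified variance still includes the between-country variation that the design has removed. The test statistic is then too small on average, the true type I error falls below 5%, and some power is lost. What is at stake is the sharpness of the time-to-onset and time-to-rescue comparisons, and having one prespecified p-value rather than two candidates.

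**Working it through.** **1. The plan's own power figures.** Inputs from Protocol 9.5: 630 per group, two-sided alpha 0.05, rates 23.2% vs 15.1% (pain freedom) and 40.5% vs 32.1% (MBS freedom). Power = Φ(d/SE − 1.96), with SE = √[(p1(1−p1) + p2(1−p2))/630].
- Pain freedom: d = 0.081, SE = 0.02205, d/SE = 3.673, power 95.7% (stated 95.7%).
- MBS freedom: d = 0.084, SE = 0.02699, d/SE = 3.112, power 87.5% (stated 87.5%).
- Both, as a product: 0.957 × 0.875 = 83.7% (stated about 84%).

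These figures reproduce. They concern the percentages; there is no stated log-rank figure to reproduce.

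**2. Hand check of the conservatism.** Treat 8-hour response as binary, with regional share w and rate p, and p̄ = Σwp. The unstratified variance is proportional to T = p̄(1−p̄). The sampling variance under balanced strata is proportional to W = Σw·p(1−p). The true type I error is about 2[1 − Φ(1.96/√(W/T))]. All shares and rates are assumed. Shares 4:1:1 correspond to 420/105/105 per arm, with the largest region having the lowest rate.

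| Shares | Rates, % | T | W | W/T | Type I error, formula | Simulated, unstratified |
|---|---|---|---|---|---|---|
| 4:1:1 | 35/50/65 | 0.2444 | 0.2312 | 0.946 | 4.4% | 4.3–4.4% |
| 4:1:1 | 30/50/70 | 0.2400 | 0.2167 | 0.903 | 3.9% | 3.7–3.9% |
| equal | 35/55/75 | 0.2475 | 0.2208 | 0.892 | 3.8% | 3.7% |
| equal | 25/55/85 | 0.2475 | 0.1875 | 0.758 | 2.4% | 2.3% |

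In these scenarios the stratified test stayed at 4.8–5.1%. With no regional differences W = T; a simulation with 55% in every region gave 4.9% for both tests.

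**3. Power by simulation.** Setup: 630 per arm, exponential times read at the ten scheduled assessments from 15 minutes to 8 hours, a common hazard ratio in every region, and no rescue censoring. Hazard ratio 1.2, shares 420/105/105, 40,000 replicates:

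| Control 8-h rates, % | Spread, points | Unstratified | Stratified | Loss, points |
|---|---|---|---|---|
| equal | 0 | 56.35% | 56.34% | 0 |
| 35/45/55 | 20 | 54.9% | 56.0% | 1.1 |
| 35/50/65 | 30 | 55.7% | 58.8% | 3.1 |
| 30/50/70 | 40 | 50.2% | 55.8% | 5.6 |

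A repeat run gave losses of 3.0 points (55.5% vs 58.5%) and 5.5 points (50.5% vs 56.0%) for the last two rows.

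**4. Sensitivity to shares and rates** (hazard ratio 1.24 unless stated; 6,000 replicates).
- Equal shares, rates centred on 55%, spreads 0/20/40/60: losses 0.1, 1.3, 5.5 and 13.6 points.
- Shares 70/15/15 with the large region in the middle, spreads 20/40/60: losses 0.4, 1.9 and 5.5 points.
- Control 8-hour rates set near the protocol's 2-hour placebo figures (centres 15% and 32%; hazard ratios 1.5 and 1.33; spreads 10 to 34): losses 0.4 to 3.1 points.
- Spread 80 (15/55/95%): losses 12 points (70/15/15) to 38 points (equal shares).

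**The case against.** The strongest objection is that nothing here is an error. A test whose type I error is at or below 5% is valid. SAP 6.2 and 6.3 label these analyses supportive, and SAP 5.1 makes p-values for other secondary and exploratory endpoints unadjusted and descriptive. No power is claimed for them, and an unstratified p-value matches unstratified Kaplan-Meier curves. All of this stands, and it is why the point is an improvement and not a defect.

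It is also fair that the two kinds of analysis differ by design. The percentage takes status at one time and counts rescue and missing data as failure. The response time-to-event analyses take the first response and censor at rescue. Stratifying will not make them agree; it removes only one avoidable difference.

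The simulation is a simplification. It omits rescue censoring, although Protocol 6.9.2 permits rescue after 2 hours. It does not model time to rescue over 24 hours. It uses 630 per arm even for function, phonophobia, photophobia and nausea, which Appendix 1 restricts to subsets of the EAS. The sizes should therefore not be read across to all eight endpoints.

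Two further readings go beyond the text. One is that every percentage analysis is stratified; the country/region subgroup analysis is not. The other is that the percentage analyses reflect the full randomization scheme; they also leave out prophylactic medication use.

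**Conclusion.** The point holds as a free improvement. No strata are named for the eight log-rank comparisons, whereas the main percentage analyses of the same endpoints use country/region. The direction is clear if country/region is prognostic, and no measurable cost appears if it is not.

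The size depends on assumed regional rates and shares. With a hazard ratio of 1.2 it is about 0, 1 to 1.5, 3, and 5 to 6 points for spreads of 0, 20, 30 and 40 points; equal shares at 1.24 agree where they overlap. It is smaller when one dominant region sits mid-range (0.4 and 1.9 points for spreads of 20 and 40) and larger for wider spreads.

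A reader might infer that the planned tests are in fact conservative, or that about 6 points is the most that can be lost. The documents support neither. They give no evidence that the countries differ, and 6 points belongs to one assumed spread, with larger losses beyond it. Nor is the confirmatory inference affected: these p-values lie outside the gatekeeping sequence, so no primary or key secondary conclusion changes.

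**What to change.** In SAP 5.2.3, and in the time-to-event rows of Appendix 1, state that the log-rank p-value comes from a log-rank test stratified by country/region at randomization, using the same strata as the Mantel-Haenszel analysis of that endpoint. Leave the Kaplan-Meier curves and the quartiles by arm unchanged, and footnote that the p-value is stratified. If an unstratified test is intended, say so and give the reason. Settle this before unblinding.

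The cost is one phrase in the text, a matching entry in the table and a strata option in the program. The change aligns the log-rank test with the SAP's own analysis strata; it does not bring in the second randomization factor.

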#### 5.2.4. Safety Analysis Periods

Analysis periods	Start date/time	End date/time	Usage
Pre-treatment		Study intervention start date/time	To be used to derive baseline values and to assess the safety endpoints prior to study intervention
On-treatment safety	Study intervention start date/time	Later of (1) Study intervention start date + 9 days and (2) EOT visit date	To be used to assess the safety endpoints during treatment period
Follow-up safety	Later of (1) Study intervention start date + 10 days and (2) EOT visit date + 1 day		To be used to assess the safety endpoints of the follow-up period

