### Study Arms and Duration:

Participants will receive a single dose of zavegepant or placebo in this study. The total duration of study participation will be up to approximately 16 weeks.

Study Intervention(s)		
Intervention Name	Zavegepant (PF-07930207)	Placebo
Arm Name (group of participants receiving a specific treatment or no treatment)	Zavegepant (PF-07930207)	Placebo
Unit Dose Strength(s)	10 mg per 0.1 mL	0 mg per 0.1 mL
Route of Administration	Intranasal	Intranasal
Use	Experimental	Placebo
IMP or NIMP/AxMP	IMP	IMP

Study Arm(s)		
Arm Title	Zavegepant (PF-07930207)	Placebo
Arm Type	Experimental	Placebo
Arm Description	Participants will receive a single dose zavegepant (PF-07930207) 10 mg	Participants will receive a single dose placebo

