### **2.2.2.1. Clinical Pharmacology**

Based on the completed clinical studies of IN zavegepant, the following observations were made regarding the zavegepant PK properties. Zavegepant is rapidly absorbed ( $T_{\max}$ : 0.54 hr) following a single zavegepant 10 mg IN dose. The effective half-life of zavegepant, which is considered more clinically relevant than elimination half-life as it takes into account the entire plasma concentration-time profile, ranged from approximately 5 to 8 hours across dose levels ranging from 5 to 40 mg IN. Zavegepant exhibits less than dose proportional increases in the exposure following single IN dose administration over the dose range from 1 mg to 40 mg. No evidence of meaningful accumulation was observed across a dose range of 5 to 20 mg zavegepant IN after repeated QD administration.

The results of a DDI study showed that co-administration of sumatriptan with zavegepant IN does not result in a meaningful change in the PK of sumatriptan or of zavegepant. Co-administration of sumatriptan with zavegepant IN does not cause elevations in mean arterial blood pressure or of systolic or diastolic blood pressure greater than those observed with sumatriptan alone. Zavegepant may be co-administered with a triptan without dose frequency modification. Lack of a clinically significant effect on the exposures of EE and LNG following co-administration of zavegepant 20 mg IN and an oral contraceptive support that zavegepant is not a clinically relevant inhibitor of CYP3A4. Zavegepant may be administered with an oral contraceptive without dose frequency adjustment. A 39% increase in the  $C_{max}$  and an approximate two-fold increase in zavegepant AUC was observed in participants with moderate hepatic impairment.

Zavegepant was metabolized by recombinant CYP3A4 and to a lesser extent by recombinant CYP2D6 as shown with in vitro assays, although the overall rate of hepatic metabolism of zavegepant was very low. The human ADME study demonstrated that the primary route of elimination of zavegepant is through biliary elimination, with 84.9% of the total radioactivity recovered in feces following a [ $^{14}C$ ]-zavegepant IV dose, and the contribution of renal clearance to zavegepant elimination is minimal (<12%).

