Within 3-28 days from the Screening Visit, participants will return to the site for the Baseline (Randomization) Visit. Participants who meet all eligibility criteria may be randomized at the Baseline Visit. After randomization is completed in the IRT, study intervention will be dispensed to participants to take home for a single attack of moderate or severe pain intensity occurring up to 45 days after the Baseline (Randomization) Visit. The participants will be provided with an eCOA handheld device. The eCOA handheld device may also be referred to as a handheld or an eDiary. Once a participant experiences a migraine headache of moderate to severe intensity, they should record this in the handheld. The handheld will instruct the participant to take study intervention after the initial assessments are completed in the device. The participant will complete assessments for 48 hours after taking study intervention to record efficacy and other quality of life measures, refer to Section 8.2 Efficacy Assessments for additional information. The study personnel **MUST** instruct and train the participant on the proper use of the handheld to **ENSURE** proper understanding and use of the tool, **PRIOR** to the participant leaving the office at Baseline Visit. Baseline Visit must be completed in person. **Participants in this study may be randomized only once. Under NO circumstances may a participant be re-randomized.**

Participants should be encouraged to treat their **FIRST** qualifying migraine attack (moderate or severe pain intensity) that occurs during the Treatment Phase. If participants are unable to treat their first qualifying migraine, refer to Section 6.9.2 Rescue Medication for a list of medications that are allowed during the course of this study.

Participants will return to the site for EOT Visit (after assessments in the handheld are completed) within 7 (+2) days after administration of study intervention. The "+2" day window is included for scheduling purposes only. Every effort should be made to conduct the EOT Visit within the specified window of 7 (+2) days after administration of study intervention. At the EOT Visit, medication compliance and monitoring of safety assessments will be performed as indicated in the SoA. If a participant has **NOT** treated a migraine attack with study intervention within 45 days after randomization, they are still required to complete

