all EOT Visit procedures. All participants must return used and unused study intervention and their handheld device to site. Certain provisions may be implemented, in order to minimize potential hazards to the participants due to COVID-19 **ONLY** at the EOT Visit. These provisions may allow alternatives to in-person study visits and include but are not limited to the following: conducting remote study visits via phone/telemedicine video, focusing on safety assessments during remote visits, performing safety labs via local labs or professional in-home phlebotomy vendors, and shipping of study intervention if needed. Any potential issues should be discussed with sponsor and will be addressed on an individualized basis. Components of the EOT Visit may be conducted under the provisions mentioned above (remote via phone/telemedicine, local labs, etc.), and the window visit may be extended by 5 days due to COVID-19 **ONLY** if circumstances warrant in order to minimize any potential risks to participant safety. Refer to Section 8.3.4.1 and 8.3.5.1 for additional information.

Follow-Up Visit will occur 28-35 days after treatment for safety follow-up of AEs and/or abnormal laboratory tests. Participants may be contacted via telephone. Every effort should be made to conduct the Follow-Up Visit within 28-35 days after treatment. If a participant has NOT treated a migraine attack with study intervention within 45 days after randomization, they are not required to complete the Follow-Up Visit.

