### **9.3.5. Safety Analyses**

The frequencies of the following postdose safety endpoints will be tabulated by treatment group for the safety analysis set: AEs by intensity; SAEs; AEs related to study intervention; local irritation AEs; laboratory test abnormalities by toxicity grade; and liver function test elevations.

The investigators will determine the intensity of AEs and the relationship of AEs to study intervention. The investigators' terms will be coded using the latest version of the MedDRA available at the start of the study. AEs will be presented by system organ class and preferred term.

Laboratory test results will be graded according to numeric laboratory test criteria in CTCAE if available; otherwise, results will be graded according to numeric laboratory test criteria in DAIDS Table for Grading the Severity of Adult and Pediatric Adverse Events.

Deaths will be listed without regard to onset for the enrolled analysis set.

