## 6.6.1. Adverse Events

### 6.6.1.1. AE Overview

An AE overview without SOC and PT will present the number of participants evaluable for adverse events, the number of adverse events, the number and percentage of participants with: any AE; mild AE; moderate AE; severe AE; moderate or severe AE; SAE; AE leading to study discontinuation; hepatic-related AE; potential drug abuse AE; cardiovascular AE; suicidality AE; local irritation AE; hypertension AE; Raynaud's phenomenon AE.

An AE overview will be produced by treatment group for each analysis period as defined in Section 5.2.4 using the safety analysis set. All-cause TEAEs (for on-treatment period and follow-up period) and treatment-related TEAEs (for on-treatment period) will be generated separately.

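### Treatment-related AEs starting after day 9 are tabulated only if the EOT visit was late, and no table covers AEs over the whole postdose period

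*SAP*

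**What the plan says.** Each participant takes one dose. Protocol 4.1 schedules the EOT visit "within 7 (+2) days after administration of study intervention" and adds that "the window visit may be extended by 5 days due to COVID-19". SAP 5.2.4 ends the on-treatment safety period at the "Later of (1) Study intervention start date + 9 days and (2) EOT visit date" and starts the follow-up period at the "Later of (1) Study intervention start date + 10 days and (2) EOT visit date + 1 day". The SAP sets no upper limit on the EOT date used.

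The AE tables follow these periods. For the overview, SAP 6.6.1.1 states: "All-cause TEAEs (for on-treatment period and follow-up period) and treatment-related TEAEs (for on-treatment period) will be generated separately". The SOC/PT tables (6.6.1.2) and the other significant AEs, including local irritation (6.6.1.3), are restricted in the same way. The table of TEAEs that led to leaving the study (6.6.1.4) names no period. The TEAE definition in 6.6.1.2.2 has a start but no end.

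Protocol 8.4.1 collects AEs for at least 28 days after dosing, and the Follow-Up Visit falls on days 28 to 35. Protocol 9.3.5 says: "The frequencies of the following postdose safety endpoints will be tabulated by treatment group for the safety analysis set". Its list includes AEs related to study intervention and gives no cut-off. The secondary safety endpoint (protocol section 3, SAP 3.2.2) also has no period limit. SAP 2.1 declares no modification of the protocol's analysis plan.

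**The concern.** Two things follow from the text.

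First, whether a related AE with onset after day 9 is tabulated depends on when the participant attended the EOT visit, which has nothing to do with the event. The version history gives the reason for the extension: keeping EOT visits with an extended window in the analysis. That is a sound reason for laboratory tests, vital signs, ECG and C-SSRS, which exist only at visits. AEs have their own onset dates, yet the same boundary applies to them.

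Second, the secondary safety endpoint counts participants with moderate or severe AEs, SAEs and local irritation AEs. The plan gives those counts separately for each period and never for the whole time after dosing. A reader of the study report who wants the percentage with any such event, or with any related AE, after the single dose will not find it.

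**Working it through.** **Window length.** The scheduled EOT limit is 7 + 2 = 9 days, which reproduces the 9-day minimum in SAP 5.2.4. With the COVID-19 extension it is 9 + 5 = 14 days. A later EOT visit would be a protocol deviation, although the SAP rule would still follow it.

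**Which related AEs are tabulated** (overview, SOC/PT and other-significant-AE tables):

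| Onset of related AE | EOT by day 9 | EOT on day 14 |
|---|---|---|
| Day 5 | yes | yes |
| Day 12 | no | yes |
| Day 20 | no | no |

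For an on-time participant the days with no related-AE tabulation number 28 - 9 = 19 up to the minimum collection date, or 35 - 9 = 26 up to the latest scheduled Follow-Up Visit. For EOT on day 14 the first figure is 28 - 14 = 14.

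**Why the two all-cause tables cannot be combined.** Let a participants have an event in the on-treatment period, b in follow-up, and c in both. The number of unique participants is a + b - c. The tables give a and b but not c, so the endpoint over the whole postdose period is known only to lie between the larger of a and b and the sum a + b.

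**Effect of late visits on the on-treatment percentage.** The documents give neither the share of late visits nor the background AE rate, so both are assumed. Take a constant background hazard with 28-day risk R: h = -ln(1 - R)/28 and P(d) = 1 - exp(-h × d). If a share f of an arm has EOT on day 14 instead of by day 9, the arm's percentage changes by f × [P(14) - P(9)]. The last column multiplies this by 630, the planned evaluable number per arm.

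| R (assumed) | P(9) | P(14) | f (assumed) | Arm-level change | Per 630 |
|---|---|---|---|---|---|
| 5% | 1.64% | 2.53% | 5% | 0.04 points | 0.3 |
| 10% | 3.33% | 5.13% | 10% | 0.18 points | 1.1 |
| 20% | 6.92% | 10.56% | 20% | 0.73 points | 4.6 |

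For a single participant with EOT on day 14 the window is 14/9 = 1.56 times as long. At arm level the change is small.

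**Protocol against SAP.** Protocol 9.3.5 sets out postdose tabulation of related AEs. SAP 6.6.1.1 to 6.6.1.3 set out on-treatment tabulation of them. The second is narrower than the first, and SAP 2.1 does not list it as a change.

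**The case against.** The best defence is that little is lost. Every participant with EOT by day 9 has the same window. All-cause TEAEs, TEAEs by severity, SAEs and local irritation AEs are tabulated in both periods, and the periods together cover all postdose time. The version history openly records that treatment-related AEs were removed for the follow-up period, and protocol section 9 lets the SAP modify the protocol's analyses, with an amendment required only for major changes to the primary endpoints. All of this stands. It leaves an incomplete entry in SAP 2.1, related AEs with no late tabulation, and no pooled count.

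A reader might go further in four ways that the documents do not support.

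- That window length varies freely between participants, with a day-28 visit collecting 28/9 = 3.1 times the background events. The protocol allows day 14 at most, so this describes a deviation.
- That an AE which delays the EOT visit lengthens its own window. Such an AE would usually have started by day 9 and so falls inside the common window anyway.
- That the effective half-life, which "ranged from approximately 5 to 8 hours across dose levels ranging from 5 to 40 mg IN", makes the window wrong. Nine days is 216 h, or 27 to 43 half-lives, but neither document ties the safety period to pharmacokinetics. A short half-life suggests, if anything, that few related AEs would start after day 9.
- That the secondary safety endpoint is lost. Relatedness is not part of it, and its AE components are tabulated; only the count over the whole postdose period is missing.

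Ending the AE period at day 9 while the laboratory period runs to the EOT visit would also do harm. SAP 6.6.2.2 requires a liver-test elevation and the matching AE to fall in the same safety analysis period. With split periods, a day-12 ALT rise with nausea from day 11 would no longer clearly qualify.

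**Conclusion.** The point holds as a gap in safety reporting. For on-time participants, related AEs starting in the last 19 of the 28 guaranteed collection days enter none of the related-AE tables in SAP 6.6.1.1 to 6.6.1.3, while the same events up to day 14 do enter them for participants with a permitted late visit. No table counts each participant once over the whole postdose period. This follows from the wording alone and does not depend on how many visits run late.

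The documents do not show material bias between arms. The trial is randomised and double-blind, so late visits should be roughly balanced. Under the assumptions of 5% to 20% late visits and 5% to 20% background risk, an arm's all-cause on-treatment percentage moves by 0.04 to 0.73 points. How many related AEs would start after day 9 cannot be estimated from the documents. The change is worth making because it is cheap and brings the SAP back in line with protocol 9.3.5.

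**What to change.** In SAP 6.6.1, add tables by treatment group, for the safety analysis set, covering dosing through the Follow-Up Visit and counting each participant once: all-cause TEAEs, treatment-related TEAEs, moderate or severe AEs, SAEs and local irritation AEs. State that these tables report the AE components of the secondary safety endpoint.

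Keep the existing period tables and the periods in SAP 5.2.4 unchanged, so that late EOT laboratory, vital-sign, ECG and C-SSRS data stay in the analysis and the same-period rule in 6.6.2.2 still works.

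If the sponsor prefers to keep related AEs to the on-treatment period only, SAP 2.1 should declare this as a modification of protocol 9.3.5.

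The cost is a few extra tables from data already collected. No participant procedure or existing table changes.
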